in children for open wounds. We know from our previous study and publication that the STAR particles make miniscule punctures in the skin allowing a drug applied after can only enter the skin through these tiny pores that quickly seal. Using the STAR particles will be less invasive than any open wound a child could present with who would normally be receiving LET gel prior to suture closure or instrumentation of the wound. There would be no way that when LET gel delivered at the appropriate dose could ever enter the skin and overdose a patient than delivering it through any open wound that the LET gel is already approved for.

We realize that it is not uncommon for the FDA to test drugs or devices in adults (to assess safety and efficacy) prior to children, however, there would be no endpoint to determine if the STAR particles with LET gel is efficacious in adults, as few adults will be as interested or concerned with pain or local anesthesia.

4. Study Endpoints

A. Primary

- 1) Determine the T_{SP} of the STAR particle (10% concentration and 500 μm length) in children and compare to the T_{LET} and determine which application results in a more rapid time for local anesthesia.

B. Secondary

- 1) Determine the TEWL (trans epidermal water loss) measurement before and after application of the STAR particles and compare to the TEWL measurement before and after application of the aloe gel.

5. Study Intervention/Investigational Agent

This is a single-center study to compare the time to local anesthesia following application of STAR particles applied prior to skin application of topical lidocaine (LET gel) to application of topical lidocaine (LET gel) alone at one location in 25 healthy children, adolescents and young adults.

The investigational agent will be STAR particles made of titanium dioxide, a widely-used and safe ceramic material found in sunscreens, cosmetics, and paint. The particles will vary in concentration and length in order to find the optimal concentration and length. The star-shaped geometry is designed to inhibit complete insertion of the particle into skin so STAR particles do not remain embedded in the skin. After the arms of the STAR particle puncture the skin, the elastic forces of the skin push the particles out.

6. Procedures Involved

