After signing the informed consent form, eligible participants will be enrolled in the study. At the visit, the TEWL will be measured using a wireless, portable Vapometer (Delfin Technologies, Finland) on the volar surface of the forearm where the STAR particles will be applied. The STAR particle (in aloe gel) will be delivered to the skin immediately prior to the LET gel so that the time to achieve anesthesia for the topical lidocaine (LET gel) after STAR particle application (T_{SP}) can be compared to the time to achieve anesthesia for application of topical lidocaine (LET gel) alone (T_{LET}). The STAR particle will always be applied to the participant's right arm but the order of applying STAR particle will be randomized by a computer-generated random sequence. After application of the STAR particles, and prior to applying the LET gel, TEWL will again be measured using the wireless, portable Vapometer (Delfin Technologies, Finland).

The same procedure of measuring the TEWL will be followed on the forearm not receiving the STAR particle application (Aloe gel).

A. LET Gel after STAR Particle Application (Right Arm):

Topical lidocaine (0.5 grams of Lidocaine in LET gel) will be applied immediately after applying a STAR particle preparation to the volar surface of the mid-forearm at two locations (right antecubital fossa and right wrist). Immediately after application of the STAR particles, the topical lidocaine (LET gel) will be applied. Immediately after the topical lidocaine (LET gel) is applied, pain will be assessed by the investigator every minute using the Pin-Prick Pain test. The time that the subject reports no pain (complete local anesthesia) will be recorded as the time to achieve anesthesia for the topical lidocaine after STAR particle application (T_{SP}) at both sites.

B. LET GEL Application without STAR Particle Application (Left Arm):

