Topical lidocaine (0.5 grams of Lidocaine in LET gel) will be applied immediately after applying aloe gel (CONTROL) to the volar surface of the mid-forearm at two locations (right antecubital fossa and right wrist). Immediately after application of the aloe gel, the topical lidocaine (LET gel) will be applied. Immediately after the topical lidocaine (LET gel) is applied, pain will be assessed by the investigator every minute using the Pin-Prick Pain test. The time that the subject reports no pain (complete local anesthesia) will be recorded as the time to achieve anesthesia for the topical lidocaine without STAR particle application (T_{LET}) at both sites.

The physician will also evaluate local tolerability by assessing the topical lidocaine (LET gel) alone and topical lidocaine (LET gel) post-STAR particle application site for acute skin reactions (ASRs), AEs, and SAEs on the day of application, 1 hour [± 5 minutes] after the application, 24-hours after

Protocol Title: Rapid local anesthesia by lidocaine administered using STAR particles

application, one week after application, and 30 days after application. Specifically, the participant (and parent) will report if the participant’s skin has erythema, edema, blistering, tenderness, bleeding, bruising, or any type of skin change. ASRs will be scored quantitatively with qualitative remarks as needed. ASRs, AEs, and SAEs of interest will be recorded.

7. Data Specimen Banking

This study will not be banking any specimens or data.

8. Sharing of Results with Participants

There are no expected incidental findings for the study. Results will not be returned to the participant.

9. Study Timelines

- Each subject will participate in the study for the one visit with phone follow-up one day to 30 days after the study visit.
- The duration anticipated enrolling all study participants is 2-3 months.
- The estimated date for the investigators to complete this study (complete primary analyses) is 12 months.

Study Procedures and Assessments

Procedures and Assessments	Study Visit	Follow-Up (24-hrs – 30 days)
Informed consent	X	
Medical history	X	
Inclusion and exclusion criteria	X	
STAR & Lidocaine application by clinician	X	
topical lidocaine (LET gel) application by clinician	X	
TEWL measurement before and after application	X	
Application site pain by VAS	X	
Application site pain by report	X	
ASRs, SAEs & AEs of interest	X	X

10. Inclusion and Exclusion Criteria

Inclusion criteria:

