We hypothesize that the STAR particles will not remain in the skin. Our previous research on STAR particles suggests that the risk for application of STAR particles to be minimal (1). The only AE discovered in studying patients receiving a STAR particle application has been transient local erythema and otherwise, has been very well tolerated in healthy human participants. The article published in Nature Medicine can be referenced (Tadros AR et al. STAR particles for enhanced topical drug and vaccine delivery. Nature Medicine. 2020, 26: 341–347.) The composition of the gel that will be used to formulate the STAR particles will be aloe gel. We are not aware of any risks posed by aloe gel, with the exception of the extreme rare cause of allergic or anaphylactic reaction. This aloe gel does not pose any obvious risks and is contained in numerous products such as skin lotions and hair products. These particles are made of titanium dioxide, a widely-used and safe ceramic material found in sunscreens, cosmetics, and paint. STAR particles are designed to incorporate invisibly into topical formulations applied to skin similarly to conventional topical skin products.

The local anesthetic we are evaluating (LET gel) is approved in children for open wounds. We know from our previous study and publication that the STAR particles make miniscule punctures in the skin allowing a drug applied after can only enter the skin through these tiny pores that quickly seal. Using the STAR particles will be less invasive than any open wound a child could present with who would normally be receiving LET gel prior to suture closure or instrumentation of the wound. There would be no way that when LET gel delivered at the appropriate dose could ever enter the skin and overdose a patient than delivering it through any open wound that the LET gel is already approved for.

The LET gel delivered will be minimal, applied over a small surface area and below the limit of what would cause an adverse event even if that amount of LET gel was injected locally. The dose of the application will be 100-500 mg of LET gel to the skin which is far below toxic doses. The LET gel is FDA-approved for children 2-years and older and is used in individuals who need a local anesthetic and have an open wound. There have been no reports of adverse reactions or events associated with LET gel, however, an allergic reaction or even anaphylaxis, are always potential possibilities.

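### The dosing instruction in Section 6 is a mass of lidocaine, the dose in Section 15 is a mass of gel, and no gel strength is given to reconcile them

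*Protocol*

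**What the plan says.** The dose appears in two parts of the Protocol.

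- **Section 6A (right arm, STAR particles then LET gel):** "Topical lidocaine (0.5 grams of Lidocaine in LET gel) will be applied immediately after applying a STAR particle preparation".
- **Section 6B (left arm, aloe gel then LET gel):** "Topical lidocaine (0.5 grams of Lidocaine in LET gel) will be applied immediately after applying aloe gel (CONTROL". The amount and wording match 6A.
- **Section 15 (Risk to Participants):** "The dose of the application will be 100-500 mg of LET gel to the skin which is far below toxic doses". The same paragraph calls the amount "below the limit of what would cause an adverse event even if that amount of LET gel was injected locally".

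Sections 6A and 6B both place the gel "to the volar surface of the mid-forearm at two locations (right antecubital fossa and right wrist", so each arm has two treated sites. Neither section says whether 0.5 g is for one site or for the arm. Section 15 does not say whether its application is a site, an arm or a participant. The Protocol nowhere gives the lidocaine concentration of the gel.

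**The concern.** Section 6 gives a single mass of active drug. Section 15 gives a five-fold range of product mass. These are different quantities, and without a gel strength neither converts into the other. Section 6 is the text that staff follow when dosing participants aged 10 to 21, some of them minors. Section 15 is the text on which the safety of the dose is argued. If the two do not describe the same amount, the safety statement is not shown to cover the dose prescribed.

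The dose is a protocol item, and an analysis plan would not be expected to settle it. The figure appears twice in Section 6 in clean prose, so a fault in text extraction is not a likely explanation.

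**Working it through.** **Inputs**

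- Section 6A and 6B: L = 0.5 g = 500 mg of lidocaine, per site or per arm (not stated).
- Section 15: G = 100 to 500 mg of LET gel, per site, per arm or per participant (not stated).
- Sites: two per arm, two arms, so 2 × 2 = 4 per participant. This takes the Section 6B sites as left-arm sites, as its heading says, although its text names right-arm locations.

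**Formula.** Lidocaine fraction that the gel must have for both statements to hold = lidocaine mass / gel mass, over the same sites.

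**Common basis** (both per site, or both per arm)

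- Top of the Section 15 range: 500 / 500 = 100%.
- Bottom: 500 / 100 = 500%, which is impossible.

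**All bases, as participant totals.** Section 6 gives 2 × 500 = 1000 mg of lidocaine if per arm, and 4 × 500 = 2000 mg if per site. Section 15 gives 100 to 500 mg of gel if per participant, 200 to 1000 mg if per arm, and 400 to 2000 mg if per site.

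| Section 15 basis | Section 6 per arm: fraction at top / bottom of range | Section 6 per site: fraction at top / bottom of range |
|---|---|---|
| Participant | 1000/500 = 200% / 1000/100 = 1000% | 2000/500 = 400% / 2000/100 = 2000% |
| Arm | 1000/1000 = 100% / 1000/200 = 500% | 2000/1000 = 200% / 2000/200 = 1000% |
| Site | 1000/2000 = 50% / 1000/400 = 250% | 2000/2000 = 100% / 2000/400 = 500% |

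The lowest fraction is 50%, in one cell and only at the 500 mg end. Two cells reach exactly 100%, again only at that end. Every other entry exceeds 100%.

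**If Section 6 means 0.5 g of gel.** Two features of the text favour this. The Protocol uses topical lidocaine as its name for the product, for example "Immediately after application of the STAR particles, the topical lidocaine (LET gel) will be applied" in Section 6 and "applied prior to skin application of topical lidocaine (LET gel) to application of topical lidocaine (LET gel) alone" in Section 5. And 0.5 g of gel is exactly the top of the Section 15 range. With an application read as one site:

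- 0.5 g per site = 500 mg per site, within 100 to 500 mg. Participant total 4 × 0.5 = 2.0 g of gel.
- 0.5 g per arm, split evenly over two sites = 500 / 2 = 250 mg per site, within 100 to 500 mg. Participant total 2 × 0.5 = 1.0 g of gel.

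The conflict between sections then largely goes. Two things remain: a fixed amount in Section 6 set against a range in Section 15, and a participant total that is either 1.0 g or 2.0 g.

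**The case against.** The strongest reply is that this is a slip whose intent is clear. Read as 0.5 g of gel, Section 6 lies within Section 15 on the natural per-site reading, whether 0.5 g is per site or per arm. Investigators would also be likely to notice the volume that the literal reading calls for. The study is single-center with one visit and 25 participants, the investigators perform all procedures (Section 23), and the principal investigator reviews the procedures with the team (Section 24). That staff would in practice apply differing amounts is therefore speculation. All of this stands, and it limits the weight of the point. It does not make the written instruction correct, and nothing else in the Protocol reconciles the two statements.

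A second reply is that four sites is not certain, because Section 5 speaks of one location. That phrase may simply mean the study site. Section 6, which sets the procedure, names two sites on each arm, so the four-site count is taken from there.

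A reader might infer stronger conclusions that the document does not support:

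- **That the dose exceeds the Section 15 maximum two- or four-fold.** On the gel reading, 1.0 / 0.5 = 2 and 2.0 / 0.5 = 4 arise if an application means the whole participant. A two-fold excess, 2.0 / 1.0 = 2, also arises if it means one arm and 0.5 g is per site. Nothing in Section 15 favours these readings over the per-site one.
- **That only a pure lidocaine gel could reconcile the sections.** This holds on a common basis. The mixed basis in the table brings it to 50%.
- **That participants would be overdosed by some stated multiple.** Any such multiple needs a gel strength, which the Protocol does not give.
- **That the comparison of T_SP with T_LET is biased.** The wording of the dose is the same on both arms, so no imbalance follows from it.

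**Conclusion.** The drug-mass and gel-mass statements contradict each other as written. They are compatible only at the 500 mg end of Section 15, and only for a gel of 100% lidocaine on a common basis or 50% on the most favourable mixed basis. The Protocol supports neither strength. The likely explanation is a slip for 0.5 g of LET gel, but only the sponsor can confirm that.

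The missing per-site or per-arm basis is closer to absent detail than to an error. It should be settled in the same amendment, because on the gel reading it leaves the participant total at 1.0 g or 2.0 g, a two-fold difference, and leaves unclear what total the safety statement covers.

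The point should be fixed: it concerns the operative dosing instruction in a study that includes minors, and the correction is cheap. It shows no safety shortfall and no effect on the primary comparison. The result rests on the figures as worded and on four treated sites per participant. No assumed gel strength is used.

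**What to change.** 1. The sponsor confirms the intended dose.
2. In Sections 6A and 6B, replace the lidocaine mass with one fixed mass of LET gel per site, the same at all four sites, and state the lidocaine concentration of the gel.
3. In Section 15, replace the 100 to 500 mg range with that amount, say that it is per site, and give the safety statement for the participant total over four sites.

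The cost is a wording amendment to Sections 6A, 6B and 15 and a recheck of the safety statement against the four-site total. Design, sample size and analysis do not change.

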Lidocaine delivery into skin is blocked by the skin's stratum corneum barrier. To address this limitation, collaborators at Georgia Tech developed STAR particles, which are millimeter-scale particles with micron-scale projections made of biocompatible materials that painlessly disrupt the stratum corneum. These particles are made of titanium dioxide, a widely-used and safe ceramic material found in sunscreens, cosmetics, and paint. The STAR particles have no more risk for causing an adverse or serious adverse event than those of regularly used over-the-counter skin products. STAR particles are designed to incorporate invisibly into topical formulations applied to skin similarly to conventional topical skin products. The composition of the gel that will be used to formulate the STAR particles will be aloe gel. We are not aware of any risks posed by aloe gel, with the exception of the extreme rare cause of allergic or anaphylactic reaction. This aloe gel does not pose any obvious risks and is

contained in numerous products such as skin lotions and hair products. As STAR particles are rubbed on skin, their microscopic projections create micron-scale pores in the stratum corneum to increase skin permeability to topical compounds independent of physicochemical properties. STAR particles are designed small enough to be painless and hard to see, but large enough to enable delivery of molecules like lidocaine into skin. A STAR particle micro-projection length of a few hundred microns with a tapered geometry provides mechanical strength with a sharp tip (<10 μm radius) to facilitate insertion into skin without pain. The star-shaped geometry is designed to inhibit complete insertion of the particle into skin so STAR particles do not remain embedded in the skin. After the arms of the STAR particle puncture the skin, the elastic forces of the skin push the particles out. From our previous publication, the only adverse effect from the use of STAR particles was local erythema (Tadros AR et al. STAR particles for enhanced topical drug and vaccine delivery. *Nature Medicine*. 2020, 26: 341–347.).

The use of LET gel (Edge pharma, London) is indicated for topical anesthesia

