- The study will be explained thoroughly to the participant and the participant will be allowed to ask questions. The study team will give ample time to the potential participants to ask questions and decide whether they would like to participate. The participants will be reminded that the study is completely voluntary and that not participating will not affect their care for their medical condition. The staff performing the informed consent process will also ask the participant questions to verify understanding of the information relayed.

Non-English-Speaking Participants:

We will not enroll any non-english speaking participants since we are not able to get certified translations of the study questionnaire.

This study will need a partial HIPAA waiver for recruitment purposes ONLY (i.e. identifying potentially eligible subjects). As subjects are contacted, HIPAA authorization will be obtained.

23. Setting

The research will be conducted at the Emory Childrens Center (ECC) on the Emory University campus. All procedures will be performed by the study investigators when subjects are present for visits. Subjects will be in contact (email/phone) with the PI to report any unexpected issues relating to STAR particle placement or skin, if it occurs when not at the ECC for a visit.

All research procedures will be performed at the Emory Childrens Center on the Emory University campus.

24. Resources Available

We are performing this study as a feasibility study and believe we have enough resources (Emory/CHOA outpatient Endocrine clinic) to recruit the number of subjects we seek to study.

[name], MS will devote 15% time to this study.

The PI (medical physician) and the research study team will be monitoring the subjects and subjects will be able to contact the study team for any potential consequences that could come about from the research.

The PI will review the protocol and procedures with the research study team.

25. Multi-Site Research When Emory is the Lead Site

N/A

26. References

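### Time to anesthesia is a participant's own report, taken by an investigator who knows from the fixed right-arm rule which product is under the pin, and no masking is described

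*Protocol*

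**What the plan says.** Section 4 of the protocol makes the primary endpoint a comparison of T_SP with T_LET: "compare to the T_{LET} and determine which application results in a more rapid time for local anesthesia". Section 6 (A and B) defines both times in the same way. After LET gel is applied, "pain will be assessed by the investigator every minute using the Pin-Prick Pain test", and the clock stops on the participant's word: "The time that the subject reports no pain (complete local anesthesia) will be recorded".

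The opening of Section 6 fixes the side: "The STAR particle will always be applied to the participant's right arm but the order of applying STAR particle will be randomized". Section 23 adds: "All procedures will be performed by the study investigators when subjects are present for visits". No separate assessor is named, and the protocol does not mention masking of participant, applier or tester.

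The control is not bare LET gel. Section 6B has plain aloe gel applied first, and Sections 3 and 6 give aloe gel as the STAR vehicle. Section 3 also says: "STAR particles are designed to incorporate invisibly into topical formulations applied to skin similarly to conventional topical skin products".

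**The concern.** A self-reported endpoint taken at one-minute steps depends on how hard the tester presses, how the question is put, and when the participant is ready to say that nothing hurts. Each can move with knowledge of the product. Because STAR is on the right arm in everyone, anyone who has read the protocol has that knowledge at every prick.

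Randomizing the order does not help: it balances sequence effects but leaves the product tied to the side. Randomizing the side without masking would remove the confounding of arm with product but not the effect of expectation. This is a matter of how the visit is run, so no later analysis plan can repair it. At stake is the reading of the only primary comparison, in a trial whose team expects the faster time to be on the STAR arm.

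**Working it through.** **There is no figure to reproduce.** The protocol states no test, alpha, power, effect size or SD, and gives 25 participants without derivation.

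**Step 1: does the tester know?** No sentence says that the tester is unmasked. It follows from two statements: STAR is always on the right arm (Section 6), and the study investigators perform all procedures (Section 23). While the side is fixed, the tester cannot be masked. For the participant no such inference is available, since what participants are told is not shown.

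**Step 2: what a shift does.** Let the paired difference be T_LET minus T_SP, with true mean Δ, expectation shift b and standard deviation SD. Then:

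- expected mean difference = Δ + b
- standard error = SD/√n = SD/5 for n = 25

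The standard error falls as n grows; b does not. A larger trial would only estimate Δ + b more precisely.

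**Step 3: illustration.** From the protocol: n = 25 pairs. Assumed: a two-sided 5% paired t test, Δ = 0, SD of 5, 10 or 15 minutes, b of 1 to 5 minutes. The chance of a significant result for STAR is P(T > 2.064), where T has a noncentral t distribution with 24 degrees of freedom and noncentrality b/(SD/5) = 5b/SD. For b = 2 and SD = 10 the noncentrality is 5 × 2/10 = 1.0, and the chance is 15.9%.

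| Shift b | SD 5 | SD 10 | SD 15 |
|---|---|---|---|
| 0 min | 2.5% | 2.5% | 2.5% |
| 1 min | 15.9% | 6.9% | 5.1% |
| 2 min | 48.4% | 15.9% | 9.3% |
| 3 min | 82.1% | 30.2% | 15.9% |
| 5 min | 99.8% | 67.0% | 35.9% |

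Simulation (100,000 trials per point) gave 2.6%, 15.9%, 48.3% and 82.1% at shifts of 0, 0.2, 0.4 and 0.6 SD, in agreement with the formula.

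**Step 4: scale.** Two minutes is two assessment steps. Section 3 puts the onset of topical anesthetics at 20 to 60 minutes, so 2 to 5 minutes is between 2/60 = 3% and 5/20 = 25% of that. The smallest mean difference that reaches significance is 2.064 × SD/5, that is 2.1, 4.1 or 6.2 minutes for SD 5, 10 or 15. Differences of that order are comparable with the shifts in the table. A difference of 20 minutes would need a shift four times the largest one shown (20/5 = 4).

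**The case against.** The strongest reply has five parts.

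- **The percentages assume what they illustrate.** They put in a shift and report how often it reaches significance. This stands: they are not evidence that a shift exists, nor an estimate of this trial's error rate, and the protocol states no error rate to breach.
- **The direction is not certain.** Section 15 allows that application may be felt as unpleasant and lists tenderness as a possible reaction. A participant aware of a sore site might report freedom from pain later. This stands in part: a shift towards STAR is the more likely one, but it is not shown.
- **Participant knowledge is not documented.** This stands. Only the tester's knowledge can be inferred.
- **Masking may not hold.** The particles are rubbed in and may be felt, they have caused erythema (Sections 3 and 15), and TEWL is read after application and before LET gel, so its values may reveal the side. This limits what masking can achieve, but does not justify describing none when the control already shares the vehicle.
- **This is a first-in-humans feasibility study without stated power.** That lowers the severity. It does not remove the point, because the stated primary objective is comparative.

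A reader might also infer that any positive result would be indistinguishable from expectation. The documents do not support that. With onset at 20 to 60 minutes, a very large difference would not easily be explained by a shift of a few minutes. TEWL, an instrument reading taken on both arms, also gives objective evidence of barrier disruption, though not of anesthesia.

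**Conclusion.** The concern holds in a limited form. The primary endpoint is subjective, the tester knows the product because the side is fixed, and no masking is described although a matched vehicle is already in use. Expectation could bias the within-person difference, more likely towards STAR, and sample size would not cure it. A modest difference would be hard to interpret.

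The size of any shift is unknown. The range of 5% to over 99% in the table reflects the assumed SD and shift and nothing in the documents. It would go too far to say that the bias certainly favours STAR, that it enters in full, or that participants are known to be unmasked. For an unpowered feasibility study this is a point that should be fixed, not one that makes the trial uninterpretable.

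One related inconsistency needs reconciling but does not change the conclusion: Section 6B is headed for the left arm yet names control sites on the right.

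**What to change.** In Section 6:

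1. Remove the rule that STAR is always on the right arm, and randomize its side by a concealed code.
2. Supply STAR in aloe and plain aloe in identical coded containers, applied with the same rubbing and for the same time.
3. Do not tell the participant which arm has STAR, and screen both forearms from the participant's view during application and testing.
4. Use one standard prick and one scripted question each time.
5. Where two members of the existing team attend, have the one who neither applied the gels nor read TEWL do the pricks, without sight of the TEWL values.
6. At the end, record which arm the participant and the tester each think had STAR. Treat this as descriptive, since a correct guess may also reflect a real effect.

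The cost is small: labelled containers, a code list, a screen and a script. Items 1 to 4 need no added staff. Masking may be imperfect because of the feel of the particles, erythema and the TEWL readings. With a single operator, masking of the tester is only partial, and the report should say so.
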